6.4.6 Physical examination

A brief physical examination includes the following: cardiovascular, lungs, abdomen, and extremities; and any organ systems pertinent to the subject's signs, symptoms or adverse events.

A complete physical examination includes the following: general appearance, head, eyes, ears, nose, throat, neck, cardiovascular, lungs, abdomen, lymph nodes, extremities, neurological, skin, and musculoskeletal.

Baseline data for physical examination is collected at Week -4, and new findings at the following physical examinations are recorded as change from baseline.

6.4.7 ECG

6.4.7.1 Resting 12-lead ECG

A 12-lead ECG must be performed at Week -4, 0 and 12.

A 12-lead ECG will be taken after the subject has been lying down resting. The ECG will be evaluated by the investigator and entered as 'Normal' or 'Abnormal' in the eCRF. If the ECG is evaluated as "Abnormal" the investigator should document the specific abnormality.

6.4.8 Vital signs

6.4.8.1 Blood pressure and heart rate

For this study, sitting blood pressure/heart rate and orthostatic blood pressure/heart rate measurements are required. Sitting blood pressure will be assessed at the enrolment visit, Week -4, Period C and Week 16 and orthostatic blood pressure will be assessed at Week 0, 2, 4, 12 and 16.

Sitting Blood Pressure (BP) and heart rate

One heart rate measurement will be taken after the patient has been sitting and resting for at least 5 minutes and before blood samples are taken. The heart rate measurement will be followed by 3 blood pressure measurements, using a standardized cuff adapted to the size of the patient's arm. All 3 readings have to be recorded. For analysis the average of the 3 blood pressure readings will be used. blood pressure readings will be taken with the patients comfortably in a seated position with the arms raised to the level of the heart and in a supported position. All readings should be recorded as accurately as possible and the same blood pressure machine should be used for all assessments for a given patient.

Orthostatic Blood Pressure and Heart Rate

At selected visits where orthostatic blood pressure and heart rate are measured, measurements should be obtained following completion of seated blood pressure.

The supine blood pressure and heart rate must be measured prior to the standing blood pressure. The patient should rest in the supine position for at least 5 minutes prior to measurement of blood pressure and heart rate. Supine blood pressure will be determined from three replicate measurements obtained at least 1 minute apart. All 3 readings have to be recorded. For analysis the average of the 3 blood pressure and heart rate readings will be used.

The patient will then stand for 2 to 3 minutes. After this time, measure the blood pressure with the arm supported at the antecubital fossa at heart level. Standing blood pressure and heart rate will be determined from three replicate measurements obtained at least 1 minute apart. All 3 readings have to be recorded. For analysis the average of the 3 blood pressure and heart rate readings will be used. All readings should be recorded as accurately as possible and the same blood pressure machine should be used for all assessments for a given patient.

6.4.9 Other safety assessments

Urinary and Genital Infections

The following is presented to assist in the classification and management of infections of the urinary and genital tracts. It is not intended to supplant investigators' clinical judgment:

Asymptomatic bacteriuria is defined as the presence of $\geq 10^5$ colony forming units/mL of bacteria, in a properly collected voided urine specimen, without signs or symptoms typically attributed to urinary tract infection. Asymptomatic bacteriuria is prevalent among diabetic women, and is associated with pyuria in 70% of cases. Neither guidelines from the US

(Nicolle LE et al 2005) nor Europe (European Association of Urology 2008) recommend screening for, or treatment of, asymptomatic bacteriuria in non-pregnant diabetic patients. In this study, the central laboratory will not routinely report the results of urinary dipstick tests for leukocyte esterase as a screening test for pyuria in surveillance urine examinations.

If based on suggestive signs or symptoms (dysuria, urgency or frequency of urination, suprapubic or perineal discomfort, flank, back, or abdominal pain, costovertebral angle tenderness, nausea, vomiting, fever, chills, or sepsis) the investigator believes that a urinary tract infection may be present, urine cultures (in a local laboratory) should be obtained to confirm a presumptive diagnosis of cystitis, urinary tract infection, pyelonephritis, or prostatitis. Mid-stream clean catch urine collections are recommended. Clinical judgment and local standards of care should apply to decisions concerning therapy.

Investigational product should be held in subjects with clinical evidence of upper tract UTI (e.g. pyelonephritis) or presumed urosepsis until the course of treatment of the infection has been completed and clinical recovery has occurred. It is recommended that a follow-up urine culture is obtained within 7 days of clinical recovery from a documented urinary tract infection.

Also, it is the investigator's responsibility to report, as applicable based on investigator's judgment and subject's medical history, related adverse events as defined in Section 6.4.3. Additional information, including but not limited to completion of supplemental eCRFs may be requested for certain adverse events and/or laboratory abnormalities which are reported/identified during the course of the study.

Hypoglycemic events

The subject will be asked to always self-monitor fasting blood glucose in case of symptoms suggestive of hypoglycaemia and to register any signs of hypoglycaemia in the supplied subject's card.

A hypoglycaemic event can be either

- An episode with symptoms and confirmed low glucose.
- An episode with low glucose.
- An episode with symptoms when glucose was not measured.

For the evaluation of hypoglycaemic events special attention will be given to as described below.

- Major hypoglycaemic events, defined as symptomatic events requiring external assistance due to severe impairment in consciousness or behaviour, with a capillary or plasma glucose value <3.0 mmol/L (<54 mg/dL), and prompt recovery after glucose or glucagons administration.

- Minor hypoglycaemic event, defined as either a symptomatic event with a capillary or plasma glucose value <3.5 mmol/L (<63 mg/dL), and no need for external assistance, or an asymptomatic blood glucose measurement <3.5 mmol/L (<63 mg/dL).
- Events suggestive for hypoglycaemia, with symptoms that the subject experiences as hypoglycaemia and no confirmative measurement.

Data to be collected for each hypoglycaemic event:

- Date of start and stop and time of the day for start
- If symptoms are present or not and which symptoms
- If finger stick value obtained and the plasma glucose value
- Intervention needed for recovery, max intensity, action taken, causality and possible contributing factors
- Time of last drug administration
- Time of last meal

The subject's card will be reviewed and data regarding hypoglycaemic events transcribed into the eCRFs at each clinical visit. A new subject's card for the next period will be handed over to the subject. If a major hypoglycaemic event occurs, or more than one minor event since last visit, the subject should contact the investigator. For recording of hypoglycaemic events/symptoms suggestive of hypoglycaemic events as AEs, see Section 6.4.3.

Hyperglycemic events

Fasting plasma glucose(FPG) will be measured at each visit. For the visits which pre-specified glycemic parameters on FPG are established (See Table 6), subjects are checked whether they have lack of glycemic control/hyperglycemic events.

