5.8 Discontinuation of investigational product

5.8.1 Criteria for discontinuation from the study

Subjects may be discontinued from study treatment and assessments at any time. Specific reasons for discontinuing a subject are:

- Voluntary discontinuation by the subject who is at any time free to discontinue his/her participation in the study, without prejudice to further treatment
- Risk to subjects as judged by the investigator and /or AstraZeneca and/or Bristol-Myers Squibb
- Severe non-compliance to protocol as judged by the investigator and/or AstraZeneca
- Incorrect enrolment, ie, the subject does not meet the required inclusion/exclusion criteria for the study
- Incorrectly randomized subjects, where appropriate following discussion between investigator and study team physician
- Subject lost to follow-up
- Adverse Event (including laboratory abnormality or intercurrent illness) which, in the opinion of the investigator, indicates that continued participation in the study is not in the best interest of the subject
- Development of study specific discontinuation criteria listed below
 1. Use of (need for) any anti-hyperglycaemic medication other than investigational product, except of insulin for ≤ 5 days during a hospitalization due to any reason.
 2. Requirement for oral glucocorticoid therapy that will involve ≥ 5 days of therapy
 3. Major and/or frequent hypoglycaemic events, defined as ≥ 1 major event or recurring minor events (any recurrent events of hypoglycaemia, as judged by the investigator, not meeting the definition of major hypoglycaemic event) and if

contributing factors (eg, excessive physical activity) have been evaluated. See Section 6.4.3 for definition of hypoglycaemic events.

4. CK >10 x ULN confirmed at a repeated measurement, preferably within 24 hours, but not exceeding 72 hours, see Section 5.8.2 for further guidance
5. Increase of ALT and/or AST >5 x ULN more than two weeks after initiation of close monitoring of ALT and/or AST, see Section 5.8.2 for further guidance
6. Increase of ALT and/or AST >3 x ULN and increase of Total Bilirubin (TB) >1.5 x ULN confirmed at a repeated measurement within 72 hours, see Section 5.8.2 for further guidance
7. Increase of ALT and/or AST >8 x ULN confirmed at a repeated measurement within 72 hours, see Section 5.8.2 for further guidance

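### The hypoglycaemia contact rule in Section 6.4.9 does not call for contact after a single event needing external assistance if glucose was 54-62 mg/dL, was below 54 mg/dL without prompt recovery, or was not measured

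*Protocol*

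**What the plan says.** The hypoglycaemia part of Protocol Section 6.4.9 sets up three classes of event.

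- **Major**: a symptomatic event in which severe impairment made external assistance necessary, "with a capillary or plasma glucose value <3.0 mmol/L (<54 mg/dL), and prompt recovery after glucose or glucagons administration".
- **Minor**: either "a symptomatic event with a capillary or plasma glucose value <3.5 mmol/L (<63 mg/dL), and no need for external assistance", or an asymptomatic reading below the same 63 mg/dL limit.
- **Suggestive**: "Events suggestive for hypoglycaemia, with symptoms that the subject experiences as hypoglycaemia and no confirmative measurement".

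The instruction to the subject uses only the first two: "If a major hypoglycaemic event occurs, or more than one minor event since last visit, the subject should contact the investigator". Otherwise the subject's card is reviewed and "data regarding hypoglycaemic events transcribed into the eCRFs at each clinical visit".

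Section 5.8.1, criterion 3, lists major or frequent hypoglycaemia as a reason for discontinuation. There, recurring minor events are explained more widely than in Section 6.4.9: any recurrent hypoglycaemia that is not major counts, in the investigator's judgement.

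**The concern.** The two classes that drive the contact instruction leave a space between them. Needing help takes a symptomatic event out of the minor class, but does not put it into the major class unless glucose was also below 54 mg/dL and recovery was prompt. Slow recovery, which is clinically worse, takes an event out of the major class. A failure to measure, which is plausible in a severely impaired subject, does the same.

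What is at stake is when the site learns of the event. The investigator can stop treatment for risk, and Section 6.4.4 requires serious adverse events to be reported quickly, but both start only once the investigator knows. The contact sentence is the trigger that Section 6.4.9 provides between visits. Under Section 6.4.3, non-serious hypoglycaemia is also kept off the adverse event page, so card review is the stated route for these episodes.

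**Working it through.** The protocol gives no numerical result to reproduce here. The check applies the stated definitions to each type of event and then works out the wait until card review.

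**Inputs.** The definitions and contact rule come from Section 6.4.9, and the visit days and windows from Table 2. The two unit systems agree: 3.0 × 18.016 = 54.0 mg/dL and 3.5 × 18.016 = 63.1 mg/dL.

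**Rule.** Contact if the number of major events is at least 1, or the number of minor events since the last visit is at least 2.

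| Event | Class in Section 6.4.9 | Contact after 1 event | Contact after 2 events |
|---|---|---|---|
| Assisted, 50 mg/dL, prompt recovery | major | yes | yes |
| Assisted, 50 mg/dL, no prompt recovery | none | no | no |
| Assisted, 58 mg/dL | none | no | no |
| Assisted, not measured | suggestive | no | no |
| Unassisted, symptomatic, 50 mg/dL | minor | no | yes |
| Unassisted, symptomatic, 58 mg/dL | minor | no | yes |
| Asymptomatic, 58 mg/dL | minor | no | yes |
| Unassisted, not measured | suggestive | no | no |

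Rows 2 and 5, and rows 3 and 6, compare events at the same glucose. In each pair the milder event can reach the contact threshold. The assisted one cannot do so under these definitions. Rows 4 and 8 behave alike: without a measurement the rule says nothing, with or without assistance.

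**Wait to the next card review in the treatment period.** The scheduled gap is the difference between nominal visit days. The maximum is the later visit at the end of its window minus the earlier visit at the start of its window.

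- Visit 6 to 7: 7 days; maximum (7 + 3) − 0 = 10 days.
- Visit 7 to 8: 14 − 7 = 7 days; maximum (14 + 3) − (7 − 3) = 13 days.
- Visit 8 to 9: 28 − 14 = 14 days; maximum (28 + 3) − (14 − 3) = 20 days. The later pairs up to Visit 13 have the same spacing and windows.

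The scheduled gap is thus 7 to 14 days, and at most 20 days within windows. These are full gaps between visits; an event part-way through a gap waits less.

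**The case against.** The strongest counter-argument is the wider explanation of recurring minor events in Section 5.8.1. A reader of the table might infer that no number of assisted events outside the major class can ever trigger contact. The documents do not settle that. If the Section 5.8.1 wording is carried into Section 6.4.9, two such events would count as minor and contact would follow. Against this, the wording was written for the investigator's discontinuation decision, depends on the investigator's judgement and so on prior awareness, and differs from the explicit minor definition in Section 6.4.9. Recurrence is therefore arguable. A single assisted event is left out on either reading.

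Other safeguards are real. A reader might infer that the gap prevents treatment being stopped. It does not: "Subjects may be discontinued from study treatment and assessments at any time", and one listed ground is "Risk to subjects as judged by the investigator and /or AstraZeneca and/or Bristol-Myers Squibb". Recurrent non-major events also fall expressly within criterion 3. Each episode is recorded with its glucose value, the intervention needed and its intensity. The contact sentence is a minimum, and nothing discourages an earlier call. These points limit the consequence, but most of them operate only after the site knows of the event.

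It is also tempting to add the four weeks from Week 12 to Week 16 as the longest wait. That would assume that the card is still in use then, whereas Table 1 schedules the glucose-meter procedure only to Week 12. The figure is not relied on here.

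Finally, few events are likely. Section 1.4 reports no hypoglycaemia of severe intensity in MB102008, and Table 5 prohibits other glucose-lowering drugs during the treatment period apart from short in-hospital insulin. The statement in Section 1.4 that no hypoglycaemia was confirmed is less helpful: it used a limit of 50 mg/dL or below and says nothing about 54-62 mg/dL.

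**Conclusion.** The point holds for the single assisted event. Read as written, Section 6.4.9 does not ask for contact after one event needing external assistance at 54-62 mg/dL, at below 54 mg/dL without prompt recovery, or without a measurement. For the two measured types the ordering is backwards. For unmeasured events it is an omission of the whole class, not an inversion, because there is no glucose value to match and two unassisted unmeasured events do not trigger contact either.

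The effect is a possible delay in the site's awareness, bounded in the treatment period by the visit gaps above. This assumes that the subject follows the instruction literally and does not call unprompted. The number of subjects affected cannot be derived from the protocol and is probably small. No event is lost from the record, and no efficacy result changes. Severity is minor: a cheap improvement to a safety instruction.

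**What to change.** Keep the present major definition for classification and reporting. In the contact sentence of Section 6.4.9, replace the major-event trigger with any hypoglycaemic event that required external assistance, whatever the glucose value, whether or not it was measured, and however fast the recovery. Leave the trigger for more than one minor event as it is. Give subjects matching instructions.

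The cost is one sentence and the corresponding subject material. No data item, visit or analysis is added. The downside is an occasional extra call about an episode that proves not to be hypoglycaemia.

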6.4.10 Adjudication of Cardiovascular Adverse Events

A Clinical Event Committee (CEC), blinded to the treatment of the subjects, will independently adjudicate certain cardiovascular adverse events, and they will operate in accordance with a dedicated Clinical Event Committee Charter/Manual of Operations: Dapagliflozin Program. The CEC will adjudicate events possibly related to the following events:

Death including:

- (a) Cardiovascular Death
- (b) Non-cardiovascular Death

Myocardial Infarction (MI) including:

- (a) ECG and /or cardiac enzymes confirmed MI
- (b) Sudden death
- (c) Percutaneous coronary intervention (PCI)-related myocardial infarction
- (d) CABG-related myocardial infarction
- (e) MI diagnosed via pathologic criteria
- (f) Silent MI

Fatal and Non-fatal Stroke including:

- (a) Ischemic Stroke
- (b) Hemorrhagic stroke

Serious Adverse Events of the following:

- Heart failure
- Cardiac arrhythmia
- Unstable angina
- Unplanned arterial revascularization (coronary, carotid and peripheral)
- Cardiac arrest with successful resuscitation
- Deep Vein Thrombosis and Pulmonary Emboli
- Systemic non-stroke arterial embolism/thrombosis including systemic arterial occlusion
- Non-traumatic amputation of the lower limb. Only events above the ankle will be considered for adjudication.

In order to provide the independent CEC with appropriate and adequate information for adjudication of the listed events, please consult the Reference Manual, Dapagliflozin Cardiovascular Adjudication Reference Manual for Primary Investigators and Study Staff.

6.5 Patient reported outcomes – Not Applicable

6.6 Pharmacokinetics

6.6.1 Collection of samples

Blood samples (3 mL) for determination of dapagliflozin in plasma will be taken at the times presented in the study plan (See [Table 1](#)). At visit 7, 10 and 12, plasma samples will be taken before administration of dapagliflozin. At visit 13, plasma samples will be taken at 60, 90, 120, 180 and 240 minutes after administration of dapagliflozin.

Samples will be collected, labelled stored and shipped as detailed in Laboratory Manual.

For blood volume see Section [7.1](#).

6.6.2 Determination of drug concentration

Samples for determination of drug concentration in plasma will be analysed by AtlanBio, [name] *on* behalf AstraZeneca, using liquid chromatography and mass spectrometric detection. The lower limit of quantification LLOQ of dapagliflozin in plasma is 1.0 ng/mL.

6.7 Pharmacodynamics – Not Applicable

6.8 Pharmacogenetics – Not Applicable

6.9 Health economics – Not Applicable

7. BIOLOGICAL SAMPLING PROCEDURES

7.1 Volume of blood

The total volume of blood that will be drawn from each subject at maximum in this study is as follows:

Table 8 Volume of blood to be drawn from each subject

Visit	1	2	3	4	5	6	7	8	9	10	11	12	13	14	Total
Assessment															
Haematology	2			2		2	2	2	2	2	2	2	2	2	22
Serum blood sampling ^a	10			5		13	5	5	5	10	5	5	13	10	86
HbA1c	2				2	2			2	2	2	2	2	2	18
FPG	2	2 ^b	2 ^b	2	2	2	2	2	2	2	2	2	2	2	28
Markers of bone metabolism ^c						10					10		10	10	40
PT, APTT	1.8														1.8

Table 8 Volume of blood to be drawn from each subject

Visit	1	2	3	4	5	6	7	8	9	10	11	12	13	14	Total
Assessment															
OGTT ^d						10							10		20
PK sample ^e							3			3		3	15		24
Total	17.8	2	2	9	4	39	12	9	11	19	21	14	54	26	239.8

- ^a Serum blood sampling for Clinical chemistry, Fasting Insulin, C-peptide, Fasting serum lipids (TC, LDL-C, HDL-C, TG, and FFA), Hepatitis Screen Panel (anti-HAV (IgM, IgG), HBsAg, anti-HCV, and anti-HBc), Thyroid Stimulating Hormone, Cystatine C. Blood volume depends on the assessment for each visit.
- ^b If subject treated with anti-diabetic medication up to enrolment.
- ^c Parathyroid hormone, osteocalcin, 25-vitamin D, C-terminal cross-linking telopeptides of type I collagen (CTX), Bone-specific alkaline phosphates and Procollagen type-1 N-terminal propeptide (PINP)
- ^d Visit 13, OGTT is not performed in subjects who did not perform OGTT at Visit 6, subjects who did not complete period C or subjects whose FPG is ≥ 180 mg/dL at Visit 12. At Visit 13, blood samples are drawn 60, 90, 120, 180 and 240 min after administration of 75 g oral glucose solution.
- ^e Plasma samples for analysis of dapagliflozin are obtained before administration of dapagliflozin at Visit 7, 10 and 12. At Visit 13 plasma samples are obtained at 60, 90, 120, 180 and 240 after administration of dapagliflozin. If the subjects perform OGTT at Visit 13, plasma samples are obtained simultaneously with OGTT blood samples.

7.2 Handling, storage and destruction of biological samples

The samples will be used up or disposed of after analyses.

7.2.1 Clinical chemistry/ haematology samples

Samples will be disposed after the clinical study report has been finalised.

7.2.2 Pharmacokinetic samples

Samples will be disposed after the clinical study report has been finalised.

7.3 Labelling and shipment of biohazard samples

The Principal Investigator ensures that samples are labelled and shipped in accordance with the Laboratory Manual and the Biological Substance, Category B Regulations (materials containing or suspected to contain infectious substances that do not meet Category A criteria), see Appendix C ‘IATA 6.2 Guidance Document’.

Any samples identified as Infectious Category A materials are not shipped and no further samples will be taken from the subject unless agreed with AstraZeneca and appropriate labelling, shipment and containment provisions are approved.

7.4 Chain of custody of biological samples

A full chain of custody is maintained for all samples throughout their lifecycle.

The Principal Investigator at each centre keeps full traceability of collected biological samples from the subjects while in storage at the centre until shipment or disposal (where appropriate) and keeps documentation of receipt of arrival.

The sample receiver keeps full traceability of the samples while in storage and during use until used or disposed of or until further shipment and keeps documentation of receipt of arrival.

AstraZeneca keeps oversight of the entire life cycle through internal procedures, monitoring of study sites and auditing of external laboratory providers.

